## 1. Introduction

### 1.1. Background and Rationale

The Cardiva VASCADE Vascular Closure System (VCS) is designed to deliver a resorbable collagen patch, extravascularly at the arteriotomy site to aid in achieving hemostasis. The collagen patch is designed to seal the arteriotomy within minutes and be resorbed in approximately three months. There are two versions of the product; one is for use in 5 Fr 12 cm introducer sheaths and the other for use in 6 or 7 Fr 12 cm introducer sheaths.

The safety and effectiveness of this device has been shown in several studies of retrograde access closure with very low complication rates and improved times to hemostasis and ambulation, compared to manual compression subjects (1). Results of the RESPECT Trial led to FDA's PMA approval of the Cardiva VASCADE™ VCS on Jan. 31, 2013, and it is currently commercially available in the U.S., and in Europe under the CE-mark.

The use of alternate approaches to arterial access for percutaneous transfemoral revascularization has been on the rise in the U.S. and abroad, as advances in technology have broadened treatment options for patients needing treatment in the lower extremity vasculature. Antegrade punctures of the femoral artery often require a steeper puncture angle and can be technically more challenging, especially in obese patients. However, antegrade femoral puncture is commonly performed in patients with infrainguinal vascular disease, and allows the operator to treat ipsilateral lower limb lesions with better manipulation, support and pushability of wires and catheters, when compared to femoral retrograde, cross-over access (2-5). Manual compression is still regarded as the gold standard for achieving hemostasis and is widely used in both antegrade and retrograde access, but it has long been associated with patient discomfort associated with groin pressure and prolonged immobilization (5).

Although most vascular closure devices have been routinely tested for safety and efficacy in retrograde access procedures, these same devices are being successfully used in antegrade access diagnostic and interventional peripheral procedures (6).

There have been many single-center and multi-center studies conducted to examine procedural outcomes when VCDs are used to close antegrade femoral access sites. Although the vast majority of these studies are limited to retrospective analyses, the major complication rates have been reportedly similar to those reported in retrograde evaluations with these commercial devices (4-10). However, due to major inconsistencies in study methods, definitions and reporting among currently published studies, it is difficult to make a meaningful comparison of outcomes across studies and devices (7).

Due to the growing adoption of antegrade femoral access and the use of VCDs to close these arteriotomies, it is important to collect performance and complication outcomes data related to this procedural variable. The aim of the ANTEGRADE-PVD registry is to consistently collect prospective data on procedural outcomes in antegrade access cases closed with the VASCADE VCS in a way that is consistent with the RESPECT Study design and the FDA-approved Instructions for Use (IFU).

## **1.2. Risks and Benefits**

### **1.2.1. Risks**

Risks associated with the VASCADE VCS are similar to those associated with other extravascular methods of achieving hemostasis at arteriotomy sites. Complications that may occur include:

- Allergic response
- Arterial occlusion
- Arterial thrombus
- Arterio-venous fistula
- Bleeding/oozing from the puncture site
- Bruising at wound site
- Death
- Device failure / malfunction
- Edema
- Embolization tissue (thrombus, air, calcific debris, device)
- Hematoma
- Infection
- Inflammatory response
- Intimal tear / dissection
- Laceration of the vessel wall
- Lower extremity ischemia
- Peripheral nerve injury
- Perforation of the vessel wall
- Pseudoaneurysm
- Retroperitoneal bleeding
- Thrombus formation
- Vasovagal response
- Vasospasm
- Vascular injury
- Wound dehiscence
- Wound site pain

Previous evaluations have not shown any additional risks in comparison to those associated with other compression-based hemostasis methods.

### **1.2.2. Potential Benefits**

In the RESPECT IDE Trial, demonstrated benefits of the VASCADE™

Vascular Closure System over manual compression alone to achieve hemostasis included reduced time to hemostasis and time to ambulation in both diagnostic and interventional subjects.

This registry is intended to evaluate the potential benefit of reduced time to hemostasis, time to ambulation and time to discharge in interventional subjects undergoing antegrade access, while also evaluating procedural complications. Although antegrade access is a procedural technique that is gaining favor among clinicians for the treatment of ipsilateral peripheral disease, prospective enrollment and evaluation of outcomes related to vessel closure is lacking. Data collected in this registry may benefit clinicians in decision-making related to these types of procedures.

## **2. Device Description**

The Cardiva VASCADE Vascular Closure System (VCS) is designed to deliver a resorbable Collagen Patch, extravascularly at the arteriotomy site to aid in achieving hemostasis. The collagen patch is designed to seal the arteriotomy within minutes and be resorbed in approximately three months. There are two versions of the product; one is for use in 5 Fr 12 cm introducer sheaths and the other for use in in 6 or 7 Fr 12 cm introducer sheaths.

Refer to Attachment 2: Instructions for Use for a complete description of the device, warnings and precautions, and a summary of the PMA (P120016) Summary of Safety and Effectiveness Data.

### **2.1. Device Labeling**

A copy of the Instructions for Use (IFU) will be included with the devices. The Cardiva VASCADE™ Vascular Closure Systems (VCS) are commercially labeled for sale in the United States and contain the following information:

- Product Name
- Part number
- Lot number
- Expiration (use before) date

### **2.2. Previous Clinical Experience**

VASCADE 6/7 Fr VCS was evaluated in a prospective, multi-center, randomized (2:1) clinical trial (the RESPECT Trial) in 20 sites in the United States and one site in Australia, comparing VASCADE VCS to Manual Compression (MC). The trial involved 420 patients undergoing diagnostic (n=211) or interventional (n=209) endovascular procedures.

VASCADE 5 Fr was evaluated in a prospective, single treatment, single-center study to confirm the safety and effectiveness of the scaled-down 5 Fr version of the VASCADE 6/7 Fr VCS.

Conclusions: The results from the RESPECT clinical trial demonstrated that patients who have undergone diagnostic or interventional cardiac or peripheral vascular endovascular procedures using a 6 or 7 Fr introducer sheath and were treated with VASCADE VCS have statistically and clinically significant decreased times to hemostasis and ambulation for diagnostic and interventional procedures, when compared to patients treated with manual compression. In addition, the trial demonstrated that patients treated with the VASCADE VCS were non-inferior to patients treated with manual compression with respect to major access site-related complications, with 0 (0%) major access site-related complications reported in both VASCADE and control cohorts. A confirmatory clinical study and engineering analysis demonstrated that the VASCADE 5 Fr VCS is equivalent to the VASCADE 6/7 Fr VCS in design and performance (1). Refer to Attachment 2: Instructions for Use for detailed study information.

### **3. Study Objective**

The objective of the ANTEGRADE-PVD registry is to collect procedural outcomes data when the Cardiva VASCADE™ Vascular Closure System (VCS) is used to seal femoral arterial access sites at the completion of ipsilateral peripheral interventional procedures performed through 5-7 Fr introducer sheaths via an antegrade approach. Antegrade access is experiencing growing adoption in catheter-based procedures to treat peripheral artery disease, with many advantages for lower limb procedures in particular. This post-market registry is being conducted under an FDA-approved indication for use for this device.

## **4. Study Design**

### **4.1. Overview**

The ANTEGRADE-PVD registry is a multi-center, single arm post-market registry to evaluate procedural outcomes in subjects when the Cardiva VASCADE™ Vascular Closure System (VCS) is used to seal femoral arterial access sites at the completion of ipsilateral peripheral interventional procedures performed through 5-7 F introducer sheaths via an antegrade approach.

Procedural outcomes related to performance and complications will be assessed through hospital discharge and 30 (+/- 7) days post-procedure.

### **4.2. Sample Size**

Up to 100 subjects will be prospectively enrolled in this registry.

### **4.3. Investigational Sites**

This registry will be conducted at up to 7 clinical sites in the United States.

## 5. Subject Population

### 5.1. Selection Criteria

The following pages outline the specific inclusion and exclusion criteria for the registry. Before enrollment in the registry, a patient must meet all of the inclusion and exclusion criteria requirements.

#### 5.1.1. Pre- Operative Inclusion Criteria

All subjects are required to meet the following inclusion criteria in order to be considered eligible for participation in this registry:

Pre-Operative Inclusion Criteria	
 
1. 18 to 80 years of age;
 
2. Capable and willing to give informed consent;
 
3. Acceptable candidate for an elective, non-emergent ipsilateral peripheral interventional endovascular procedure via antegrade access of the femoral artery using a 5, 6 or 7 Fr introducer sheath;
 
4. Acceptable candidate for post-procedural manual compression;
 
5. Able and willing to complete a follow-up office visit between 1-15 days post-procedure, and subsequent follow-up telephone assessment between 23-37 days;
 
6. Subject is able to ambulate at least 20 feet, with or without assistance (e.g., ambulatory amputee);
 
7. Acceptable candidate for emergent vascular surgery.
 

---	--

#### 5.1.2. Pre-Operative Exclusion Criteria

Subjects will be excluded from participating in this registry if they meet any of the following exclusion criteria prior to initiation of the endovascular procedure:

Pre-Operative Exclusion Criteria	
 
1. Advanced refusal of blood transfusion, if necessary;
 
2. Active systemic or cutaneous infection or inflammation;
 
3. Pre-existing immunodeficiency disorder and/or chronic use of
 

---	--

	
systemic steroids;
 
4. Known, significant history of bleeding diathesis, coagulopathy, or current platelet count < 100,000 cells/mm^3, baseline INR ≥1.8, or fibrinogen level less than 150 mg/dl (if received a fibrinolytic agent within prior 24 hours) based on institution's standard pre-operative lab values;
 
5. Severe co-existing morbidities having a life expectancy of less than 90 days;
 
6. Currently involved in any investigational clinical trials that have not completed their primary endpoint and/or may interfere with the conduct of this registry, per Investigator's assessment;
 
7. Previous ipsilateral femoral arteriotomy with any of the following conditions:
 
 
a. access within ≤ 10 days
 
b. any residual hematoma, significant bruising, or known associated vascular complications;
 
c. within ≤ 90 days, use of an intra-vascular closure device (i.e., Angioseal);
 
 
8. Planned / staged endovascular or surgical procedures within the next 10 days, prior to office visit (excluding planned/anticipated minor amputation);
 
9. Previous vascular grafts or surgery at the target vessel access site;
 
10. Known history of deep vein thrombosis in the ipsilateral limb within the past 30 days, unless confirmed to be resolved by ultrasound prior to enrollment;
 
11. Major amputation (i.e., above the ankle) of the ipsilateral lower extremity is planned/anticipated within the next 30 (+/- 7) days, prior to study exit;
 
12. Large pannus, which may prevent antegrade access without significant tissue displacement, in the opinion of the investigator;
 
13. Significant anemia with a hemoglobin level less than 10 g/dL or a hematocrit less than 30% based on institution's standard pre-operative lab values;
 
14. Renal insufficiency (serum creatinine of > 2.5 mg/dl);
 
15. Females who are pregnant, planning to become pregnant within 3 months of the procedure, or lactating;
 
16. Extreme morbid obesity (BMI greater than 45 kg/m^2) or

--	---

	
underweight (BMI less than 20 kg/m^2);
 
17. Known allergy/adverse reaction to bovine derivatives;
 
18. Administration of low molecular weight heparin (LMWH) within 8 hours of the procedure.

--	--

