
Pre-Operative Exclusion Criteria
	
Subjects will be excluded from participating in this registry if they meet any of the following criteria prior to initiation of the endovascular procedure:
 
 
1. Advanced refusal of blood transfusion, if necessary;
 
2. Active systemic or cutaneous infection or inflammation;
 
3. Pre-existing immunodeficiency disorder and/or chronic use of systemic steroids;
 
4. Known, significant history of bleeding diathesis, coagulopathy, or current platelet count < 100,000 cells/mm^3, baseline INR ≥1.8, or fibrinogen level less than 150 mg/dl (if received a fibrinolytic agent within prior 24 hours) based on institution's standard pre-operative lab values;
 
5. Severe co-existing morbidities having a life expectancy of less than 90 days;
 
6. Currently involved in any investigational clinical trials that have not completed their primary endpoint and/or may interfere with the conduct of this registry, per Investigator's assessment;
 
7. Previous ipsilateral femoral arteriotomy with any of the following conditions: 
 
a. access within ≤ 10 days
 
b. any residual hematoma, significant bruising, or known associated vascular complications;
 
c. within ≤ 90 days, use of an intra-vascular closure device (i.e., Angioseal);
 
 
 
8. Planned / staged endovascular or surgical procedures within the next 10 days, prior to office visit (excluding planned/anticipated minor amputation);
 
9. Previous vascular grafts or surgery at the target vessel access site;
 
10. Known history of deep vein thrombosis in the ipsilateral limb within the past 30 days, unless confirmed to be resolved by ultrasound prior to enrollment;
 
11. Major amputation (i.e., above the ankle) of the ipsilateral lower extremity is planned/anticipated within next 30 (± 7) days, prior to study exit;
 
12. Large pannus, which may prevent antegrade access without significant tissue displacement, in the opinion of the investigator;
 
13. Significant anemia with a hemoglobin level less than 10 g/dL or
 

--	--

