### 5.1.3. Intra-Operative Exclusion Criteria

Subjects will be excluded from participating in this registry if any of the following exclusion criteria occur during the intravascular procedure, prior to enrollment (i.e., prior to insertion of VASCADE VCS):

Intra-Operative Exclusion Criteria	
 
1. Use of a final introducer sheath > 12 cm (or > 15 cm in overall length), or not 5, 6 or 7 Fr diameter;
 
2. Contralateral femoral arterial access with > 5 Fr catheter that is not successfully closed with a closure device during the index procedure
 
3. Index groin involves a previously placed permanent closure device (e.g., Starclose), where the device cannot be visualized to confirm that it is at least 1 cm proximal or distal to the puncture site;
 
4. Femoral artery diameter less than 6 mm at access site;
 
5. Angiographic evidence of moderate to severe calcium, > 50% stenosis, or a stent within 1 cm of the puncture site;
 
6. Overlapping Common Femoral Vein and Femoral Artery at access site;
 
7. Presence or placement of ipsilateral venous sheath during procedure;
 
8. Antegrade arterial access site: 
 
a. is a side stick
 
b. is NOT a single anterior wall femoral puncture
 
c. is NOT below the inguinal ligament / lower half of femoral head and NOT below the inferior epigastric artery origin from the external iliac artery;
 
 
 
9. More than one ipsilateral arterial access site is required in the index limb (e.g., femoral or other);
 
10. Intra-procedural bleeding around sheath, or suspected intraluminal thrombus, hematoma, pseudoaneurysm, or AV fistula;
 

---	---

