## WARNINGS

- Do not reuse or re-sterilize. The VASCADE VCS is intended to be used once only for a single patient. Product reuse or re-sterilization, may result in transmission of infectious or blood borne diseases and/or death.
  - Do not use if components or packaging appear to be damaged or defective or if any portion of the packaging has been previously opened. Damaged or opened packages may compromise product functionality.
  - Do not use if product is beyond the expiration date. Product performance has not been established beyond the labeled shelf life.
  - Do not deploy the VASCADE Disc in a stent. Do not pull the deployed VASCADE disc through a stent. Damage to the product may occur.
  - Do not use VASCADE if access is through a previously placed permanent closure device such as a metal clip. Interference between the two closure devices may result.
  - Do not deploy the Collagen Patch if there is a suspicion that the VASCADE Vascular Closure Disc is not seated against the intimal aspect of the arteriotomy site. Partial or complete obstruction of blood flow may result.
  - Do not deploy a second collagen patch at the same access site within 90 days. Safety has not been established.
- 

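### Exclusion 7 does not screen for the attached IFU's Warning against a second collagen patch at the same access site within 90 days

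*Combined protocol and SAP*

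**What the plan says.** Criterion 7 in Section 5.1.2, repeated in the synopsis, excludes a patient with an earlier ipsilateral femoral arteriotomy in three situations:

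- 7a: "access within ≤ 10 days".
- 7b: the old site still shows hematoma or marked bruising, or is known to have had a vascular complication.
- 7c: within the last 90 days, "use of an intra-vascular closure device (i.e., Angioseal").

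Criterion 3 in Section 5.1.3 adds an intra-operative check: "Index groin involves a previously placed permanent closure device (e.g., Starclose), where the device cannot be visualized" as lying at least 1 cm from the puncture.

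Section 1.1 says that VASCADE is designed to "deliver a resorbable collagen patch, extravascularly at the arteriotomy site" and to "be resorbed in approximately three months".

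The IFU, bound into the protocol as Attachment 2, states under Warnings: "Do not deploy a second collagen patch at the same access site within 90 days. Safety has not been established".

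Under Section 7.2, patients who satisfy all pre- and intra-operative criteria may be enrolled and treated. Section 9.1.1 puts everyone who receives any part of the device in ITT. Section 9.1.2 puts everyone with collagen deployed and all entry criteria met in PP.

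**The concern.** The registry's own device carries a 90-day Warning on repeat use at one site, and no eligibility criterion asks about it. Criterion 7c shows that recent closure devices were considered and that 90 days was taken as the look-back, but for a different class of device.

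The situation is foreseeable. The synopsis calls for investigators who already close antegrade punctures with VASCADE. Exclusion 8 bars further planned procedures only for the next 10 days, and Section 7.4.2 records additional interventions planned before study exit. A patient returning to the same groin some weeks after a VASCADE closure is therefore plausible.

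Two things are at stake. The first is patient safety: on the protocol's own resorption time of about three months, the earlier patch may still be present when the second is placed, and the label says that safety in that situation is not established. The second is the meaning of the PP set, which would include use that the label warns against, because the subject met every entry criterion as written.

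**Working it through.** The plan states no figure to reproduce, so the check is a comparison of texts. The test case is a patient whose ipsilateral femoral site was closed with VASCADE between 11 and 90 days before the index procedure, has healed cleanly, and is now to be punctured at the same place.

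| Criterion | What it catches | Excludes the test case? |
|---|---|---|
| 7a | Access at day 10 or earlier | No, day 11 or later |
| 7b | Site with residual signs or known complications | No, the site is clean |
| 7c | Intra-vascular closure device, 90 days or less | No, VASCADE is extravascular (Section 1.1) |
| Pre-operative 9 | Earlier graft or surgery at the access site | No, percutaneous closure only |
| Intra-operative 3 | Permanent closure device that cannot be shown to lie clear of the puncture | No, the patch resorbs (Section 1.1) |
| Intra-operative 14 | Physician prefers another method of hemostasis | Only if the physician chooses to use it |

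No other criterion in Sections 5.1.2 or 5.1.3 mentions an earlier VASCADE or collagen patch.

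**Width of the gap.** The IFU window runs to day 90 and 7a ends at day 10, so 90 − 10 = 80 days (days 11 to 90) are not covered. If a 90-day collagen-patch limb were added, the uncovered window would be 0 days.

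**How neighbouring Warnings are handled.** The IFU also says: "Do not use VASCADE if access is through a previously placed permanent closure device such as a metal clip". Intra-operative criterion 3 deals with that subject. The IFU warns against deploying the disc in a stent, and intra-operative criterion 5 excludes "a stent within 1 cm of the puncture site". Patient-level Warnings of this kind were thus turned into screens where the authors thought of them. The protocol gives no reason for leaving the repeat-patch Warning out.

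**Analysis sets.** If the second patch is deployed, the test case enters ITT under Section 9.1.1. It also enters PP under Section 9.1.2, because collagen was deployed and no criterion was violated.

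**Timing.** Section 7.4.1 allows screening up to 8 weeks (56 days) before the procedure. A closure 40 days before screening could be 40 + 56 = 96 days old at the procedure and so outside the Warning. A closure done between screening and the procedure would be missed if the question were asked only at screening. The 90 days must therefore be counted back from the index procedure.

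**The case against.** The best reply is that the Warning is already in investigators' hands. Section 1.1 gives consistency with the approved IFU as an aim. Section 2 sends the reader to Attachment 2 for warnings and precautions. Section 7.4.3 calls for deployment by the IFU procedure, and Section 15.4 lists failure to follow the IFU as a possible reason to suspend a center. Enrollment under Section 7.2 is permissive, the investigators are experienced, and intra-operative criterion 14 lets a careful operator decline. The affected case is also narrow: same side, same site, the same kind of patch, 11 to 90 days earlier, and no residual signs.

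Most of this stands. A reader might infer that the protocol directs or endorses use against the label. The documents do not support that; what is missing is a screen. But a general pointer to an attachment, a discretionary exclusion and a possible site sanction do not do the work of an entry criterion. The numbered deployment steps, which are what Section 7.4.3 invokes, do not repeat this Warning.

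A reader might also infer that such subjects could not be identified afterwards. That does not follow. Applying 7a, 7c and intra-operative criterion 3 already requires the date of earlier access and the type of closure device. Section 7.4.1 takes an interventional history, and Section 15.2 requires evidence of eligibility in the medical record. The eCRFs are not among the documents, so what they capture cannot be judged either way.

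**Conclusion.** The gap is real and small. As written, the eligibility criteria admit a patient whom the attached label warns against treating, for 80 of the 90 days in the Warning, and only physician discretion stands in the way. This rests on reading VASCADE as neither intra-vascular nor permanent, which is how the protocol itself describes it.

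The 80 days are calendar days and measure neither patients nor risk. The documents give no frequency for repeat same-site VASCADE closure. At full enrollment of 100, each such subject would be 1/100 = 1% of the ITT denominator. No bias in time to hemostasis or in the complication rates is shown, and the registry is descriptive with no hypothesis test.

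It is tempting to score the protocol by the share of IFU Warnings carried into the criteria. That would mean little, because the answer depends on which Warnings are counted; those on packaging, expiry and reuse were never candidates for eligibility rules. The case rests on the one missing screen, which should be added because it protects patients at almost no cost.

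**What to change.** Add a limb 7d to criterion 7 in Section 5.1.2 and in the synopsis: *within ≤ 90 days before the index procedure, a collagen patch (e.g., VASCADE) deployed at the same access site*. Same access site follows the IFU and is narrower than the ipsilateral scope of the rest of criterion 7, so it avoids excluding patients whom the Warning does not concern. Confirm it on the day of the procedure.

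In Section 7.4.1, state explicitly that the interventional history records the earlier closure device, its site and its date.

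If any such subjects have already been enrolled, leave the ITT and PP definitions as they are and list those subjects separately in the report.

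The cost is one sub-criterion in two places, one added detail in the history, and the loss of a few patients with a recent same-site VASCADE closure. The planned sample size and the analyses do not change.
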